2.11 Patient-reported outcomes

Not applicable.

2.12 Biomarkers

Specified in a separate analysis plan and reported in a separate biomarker report.

2.13 Other Exploratory analyses

Chronic GvHD recurrence following completion of a taper of ruxolitinib

This analysis is performed only for patients who taper off ruxolitinib due to achieving a CR or PR. These subjects will be identified as they have reason “responder” for ruxolitinib permanent discontinuation on the exposure CRF. It’s planned to do this analysis at time of final CSR and only if sufficient number of subjects with cGvHD recurrence after tapering off occurred.

Time to recurrence is defined as the time from completion of a taper of systemic therapy until cGvHD recurrence. Patients without event will be censored at the last contact date. Kaplan-

Meier method and the Kaplan-Meier curves as well as survival probabilities at appropriate time points will be presented with 95% confidence intervals ([Brookmeyer and Crowley 1982](#)).

In case of single subjects (less than 5 subjects) with cGvHD recurrence after tapering off, data will be reported in listing only.

Systemic corticosteroid-free response rate

Systemic corticosteroid-free response rate is defined as the proportion of subjects taking no systemic corticosteroid therapy since at least 1 month (i.e. time between date of last corticosteroid drug intake and response assessment data is ≥ 30 days) and demonstrating a complete response (CR) or partial response (PR), at any time post-baseline. Subjects who didn't receive corticosteroids at baseline and still not taking corticosteroids at time of response will be considered as corticosteroid-free responder. Initiation of any new systemic therapy after cGvHD flare or recurrence, regardless when, means treatment failure and the subject is considered as non-responder. The endpoint is similar to the primary endpoint ORR, but considers all subjects who could not taper off systemic corticosteroids as non-responder regardless if they are in CR or PR, and considers all response assessments up to End of Treatment of the subject or data cut-off date.

Systemic corticosteroid-free response rate and its 90% confidence interval will be presented based on all subjects in the FAS and by subgroup of treatment naive cGvHD vs SR-cGvHD.

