- Changes implemented in this SAP version compared to previous versions are indicated in the document history table above. The major changes compared to the previous version are:
- Analyses specified that don't need to be repeated in the final CSR
- Definition of on-treatment period for safety analyses clarified, especially for subjects who tapered off ruxolitinib treatment.
- Duration of exposure incl./excl. taper off periods added in presence of subjects who tapered off ruxolitinib. Definition of dose intensity adapted accordingly.
- Definition for duration of follow-up added.
- Changes specified in the interim CSR Section 16.1.9 “changes to the analysis plan” are implemented into the SAP, which are the updated
 - Definition of duration of response and
 - Criteria for notably abnormal vital signs.
- Analyses on reduction of corticosteroid dose updated to consider data up to end of study.
- Analysis for safety disclosure updated to report events for on-treatment and post-treatment period, separately.
- Shift table for height, weight, BMI (high/normal/low) added.
- All specification for biomarker analyses moved into a separate analysis plan.
- Specification added how to identify subjects who tapered off ruxolitinib for the analysis of cGvHD recurrence following completion of a taper of ruxolitinib.
- Analysis of systemic corticosteroid-free response rate clarified for subjects who didn't receive steroids at baseline.

All decisions regarding final analysis, as defined in the SAP document, have been made prior to final database lock of the study data.

[figure not shown]

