Exploratory objective(s)	Endpoint(s) for exploratory objective(s)		

 To describe the responses from the acceptability and palatability questionnaire of ruxolitinib oral pediatric formulation 	
 Responses from the acceptability and palatability questionnaire for the oral pediatric dose formulation after Cycle 1 (first dose), Cycle 4 and Cycle 39, as applicable. 	
 Refer to Section 2.8.4.4 	Yes

 To assess pharmacokinetic (PK) / pharmacodynamic (PD) relationships 	
 Pharmacokinetic parameters derived by population PK analysis from sparse concentration-time data, e.g., AUC, Cmax, Ctrough 	
 Refer to Section 2.10 	No

 To evaluate effect of ruxolitinib on cytokines, cGvHD biomarkers and immune cell subsets 	
 Assess changes in immune cell subsets, inflammatory cytokine levels, and soluble cGvHD biomarkers. 	
 Refer to Section 2.12 	Yes (in separate report)

 To evaluate effect of ruxolitinib on markers of 	
 Assess changes in soluble markers for bone resorption and 	
 Refer to Section 2.12 	Yes (in separate report)

Objective(s)	Endpoint(s)	Analysis	Analysis incl. in final CSR
bone development in pediatric subjects	formation, including but not limited to CTX, Osteopontin, and BALP		

• To explore cGvHD recurrence following completion of a taper of systemic therapy	
• Time to recurrence, assessed for patients with completion of a taper of systemic therapy only.	
• Refer to Section 2.13	Yes

• To evaluate systemic corticosteroid-free response rate	
• Proportion of subjects who achieved OR (CR or PR) at any time point without systemic corticosteroid therapy for at least one month prior to the disease assessment.	
• Refer to Section 2.13	Yes

2 Statistical methods

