2. On-treatment period: from day of first dose of ruxolitinib to 30 days after date of last actual administration of assigned treatment.
3. ***post-treatment period***: starting at Day 31 after last administration of ruxolitinib.

Safety summaries (tables, figures) include only data from the on-treatment period with the exception of baseline data which will also be summarized where appropriate (e.g. change from baseline summaries). In addition, a separate summary for death including on-treatment and post-treatment deaths will be provided. In particular, summary tables for adverse events (AEs) will summarize only on-treatment events, with a start date during the on-treatment period (***treatment-emergent*** AEs).

However, all safety data (including those from the post-treatment period) will be listed and those collected during the pre-treatment and post-treatment period will be flagged. In analyses for the safety disclosure, all AEs collected in the post-treatment period will be included and reported separately.

Subjects who taper off ruxolitinib due to achieving a CR or PR continue efficacy and safety assessments until their EoT visit which may be only after Cycle 39 unless the subject discontinues from study earlier. Safety data from these patients collected after the last study drug intake date + 30 days and before EoT visit will not be included in any safety analyses based on the on-treatment period as defined above. Nevertheless, these data will be listed and flagged in all listings (AEs, lab, vital signs). Subject who tapered off ruxolitinib are identified as they have reason "responder" for ruxolitinib permanent discontinuation on the exposure CRF.

For subjects who tapered off study treatment and later re-started ruxolitinib treatment after a cGvHD recurrence, the on-treatment period is from date of first dose of ruxolitinib to very last dose + 30 days including the period without treatment, which are collected in the database as dose interruption. Safety data (e.g. AEs, labs) collected during this period without treatment will be included in the summary tables as treatment emergent events.

Windows for multiple assessments

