49	31	0.63	0.881	0.505	0.747
50	32	0.64	0.859	0.514	0.753

4 Change to protocol specified analyses

One exploratory analysis endpoints is added:

Chronic GvHD recurrence following completion of a taper of systemic therapy (see [Section 2.13](#)).

5 Appendix

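### SAP 2.13 finds taper completers only by permanent-discontinuation reason 'responder', so the time-to-recurrence analysis can miss patients who recurred and re-started ruxolitinib

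*SAP*

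**What the plan says.** SAP 2.13 states the intended population: "This analysis is performed only for patients who taper off ruxolitinib due to achieving a CR or PR". The only means it gives of finding these patients is the reason 'responder' "for ruxolitinib permanent discontinuation on the exposure CRF". The clock and event are then set: "Time to recurrence is defined as the time from completion of a taper of systemic therapy until cGvHD recurrence". Small numbers have their own rule: "In case of single subjects (less than 5 subjects) with cGvHD recurrence after tapering off, data will be reported in listing only".

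SAP 2.1.1 uses the same 'responder' identifier for patients who tapered off. Its next paragraph turns to patients who tapered off and re-started ruxolitinib after a recurrence. Their on-treatment period runs from first dose to very last dose plus 30 days, "including the period without treatment, which are collected in the database as dose interruption". SAP 2.4.1 names the reason under which those periods are captured: 'dose tapering following response'. The same section reads dose interruptions and permanent discontinuations from different fields of the Study Treatment CRF, each with its own reason field.

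Protocol 6.1.5 foresees the situation: treatment of a recurrence after tapering off is at the investigator's discretion and may include starting ruxolitinib again.

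The SAP introduction lists the identification rule among the changes of the current version: "Specification added how to identify subjects who tapered off ruxolitinib for the analysis of cGvHD recurrence following completion of a taper of ruxolitinib". The exposure definitions for re-starters came in with the same version.

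**The concern.** The population is meant to be everyone who completed a ruxolitinib taper because of response. The rule searches one CRF field. For a patient who recurred and went back on ruxolitinib, the SAP says that the taper is recorded in another field. Read literally, the rule does not select that patient for the taper that was followed by recurrence.

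Selection would then depend on the outcome, because a patient is left out as a consequence of having recurred and been re-treated with ruxolitinib. Every omitted patient carries an event, so the observed recurrence count can only fall, and freedom from recurrence after tapering would look better at the end of follow-up than it was. The fewer-than-5 rule adds a second effect: the omission could turn a Kaplan-Meier analysis into a listing.

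**Working it through.** The plan states no figure for this analysis, so there is nothing to reproduce. The check has two parts.

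**1. Following one patient through the rules**

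- The patient tapers off with CR or PR, recurs and re-starts ruxolitinib (allowed by Protocol 6.1.5).
- The off-drug period is stored as a dose interruption with reason 'dose tapering following response' (SAP 2.1.1 and 2.4.1).
- SAP 2.13 looks only for 'responder' in the permanent-discontinuation field.
- If the patient is still on ruxolitinib at the end, or finally stops for another reason, there is no match and the patient is not selected.
- If the patient tapers a second time and stops as 'responder', the patient is selected. SAP 2.13 has no rule on which taper then starts the clock.

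**2. Size, with assumed counts**

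The documents give no number of taper completers, recurrences or re-starters. Protocol Amendment 2 reports 46 subjects enrolled, which is only an upper bound. Let N be the taper completers, a those who recur without re-starting, and b those who recur, re-start and are omitted. There is no censoring.

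- Full set: (a + b)/N
- Current rule: a/(N − b)
- Understatement: b(N − a − b)/[N(N − b)]

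The understatement is zero if b = 0 or if every taper completer recurs; otherwise it is positive. With assumed N = 20 and a = 5:

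| b | Full set | Current rule | Understatement (points) |
|---|---|---|---|
| 0 | 5/20 = 25.0% | 5/20 = 25.0% | 0 |
| 1 | 6/20 = 30.0% | 5/19 = 26.3% | 3.7 |
| 3 | 8/20 = 40.0% | 5/17 = 29.4% | 10.6 |
| 5 | 10/20 = 50.0% | 5/15 = 33.3% | 16.7 |

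With a = 5 and b = 1 to 5, N = 15 gives 4.3 to 16.7 points and N = 25 gives 3.2 to 15.0 points.

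The Kaplan-Meier curve need not be too high at every time. With N = 20, a = 5, b = 1:

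- Omitted recurrence last: after the fifth event the rule gives 14/19 = 0.737 against 15/20 = 0.750, which is 1.3 points too low. After the sixth it gives 0.737 against 14/20 = 0.700, which is 3.7 points too high.
- Omitted recurrence first: the rule gives 1.000 against 19/20 = 0.950, which is 5.0 points too high, ending at 3.7.

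Listing rule: the curve is lost when a ≤ 4 and a + b ≥ 5. With 5, 6, 7 or 8 recurrences in all, that takes at least 1, 2, 3 or 4 omitted re-starters. If total recurrences are below 5 anyway, only the rows of the listing change.

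**The case against.** **The CRF may keep both entries.** Separate fields are not the same as mutually exclusive entries. A 'responder' entry made at the first taper might survive the re-start, and 2.1.1 places the identifier next to the re-starter paragraph, so re-starters could be meant as a subset of identified taperers. This stands as an uncertainty. Against it, the SAP says that the period is held as an interruption, and nothing in 2.13 brings in that code.

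**There may be no re-starters.** SAP 2.4.1 words the re-starter provisions conditionally, and the document history mentions such subjects without a count. This stands: zero effect belongs in the range. A reader might infer that patients have already been lost; the documents do not show that.

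**No data are lost.** Protocol 6.1.5 requires recurrence after tapering to be reported in the database, and SAP 2.4.1 lists doses with reasons for change. The analysis can therefore be repeated, which limits the harm but does not correct the rule.

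**Stronger readings that do not hold.** A reader might put the error at 25 points, by assuming that five re-starters all taper again, stop as 'responder', do not recur again and have their first recurrence discarded (5/20 = 25.0% against 10/20 = 50.0%). But 2.13 selects patients, not tapers, and does not say which taper counts, so the first recurrence may be kept.

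A reader might also see a second defect in the clock. The 2.13 heading concerns a ruxolitinib taper, while its time definition, Table 1-1 ("Time to recurrence, assessed for patients with completion of a taper of systemic therapy only") and SAP Section 4 ("Chronic GvHD recurrence following completion of a taper of systemic therapy") refer to systemic therapy. Protocol 6.1.5.2 puts the ruxolitinib taper after the patient is off corticosteroids and CNIs, so the two completion dates normally coincide. Continued prophylaxis (Protocol 6.1) could be an exception. This is a matter of wording.

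Finally, a reader might extend the problem to duration of response or the primary endpoint. Neither uses this selection rule.

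**Conclusion.** The point holds, and it is minor. The stated rule does not match the stated population for patients who recurred and re-started, and what it leaves out is related to the outcome. The consequence depends on two facts that the documents do not give: whether anyone re-started, and whether a 'responder' entry is kept at re-start. If nobody re-started, or if that entry is kept and used with the first taper date, nothing changes. Otherwise the recurrence count and end-of-follow-up proportion are too low, by 3.7 to 16.7 points under the main assumed counts, and the Kaplan-Meier output may be replaced by a listing. The analysis is exploratory, was added by the SAP, and runs only if there are enough recurrences.

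**What to change.** In SAP 2.13:

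1. Select patients with permanent-discontinuation reason 'responder' or a zero-dose interruption with reason 'dose tapering following response'.
2. Start the clock at the last nonzero dose before the first off-drug period that carries one of these two reasons, so that an earlier safety hold cannot start it.
3. Count the first recurrence after that date, whatever treatment followed.
4. Apply the fewer-than-5 rule to this combined set.

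In SAP 2.1.1, add a note that its 'responder' identifier covers only patients who did not re-start; leave the on-treatment rules as they are. As a wording clean-up, use one taper label in 2.13, Table 1-1 and Section 4. If the SAP is closed, report this in the CSR as a change to the planned analysis, as was done in Section 16.1.9 of the interim CSR.

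The cost is a few lines of text, a revised selection flag and an origin date, built from codes that the SAP says are already in the database. No new data are needed. Someone must confirm that the selected interruptions reached zero dose. If there were re-starters, the reported recurrence proportion may rise.

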2.4 Treatments (study treatment, rescue medication, concomitant therapies, compliance)

2.4.1 Study treatment / compliance

Duration of exposure to ruxolitinib will be summarized by Age group and by means of descriptive statistics. It will also be categorized into time intervals; frequency counts and percentages will be presented for the number (%) of patients in each interval.

Total daily dose, actual cumulative dose, dose intensity (DI) and relative dose intensity (RDI) will be summarized for ruxolitinib by Age group.

The number (%) of patients who have dose reductions or interruptions, and the reasons, will be summarized for ruxolitinib by Age group.

Patient level listings of all doses administered on treatment along with dose change reasons will be produced by Age group.

The Safety Set will be used for all summaries and listings of study treatment.

If more than one dose and/or formulation is assigned within one Age group, then summaries and listings will be reported by Age group as well as doses/formulation within the Age group

Duration of follow-up

The duration of follow-up time is defined as (date of last contact) – (date of first administration of investigational treatment) + 1.

Duration of exposure to investigational treatment

Duration of exposure to investigational treatment (days) = (last date of exposure to investigational treatment) – (date of first administration of investigational treatment) + 1.

If any subjects tapered off ruxolitinib and re-started ruxolitinib treatment due to cGvHD recurrence, two different definitions of duration of exposure will be distinguished:

- **Duration of exposure including taper off periods** is defined as the time from first to very last date of ruxolitinib treatment, which includes the intervening period without treatment.
- **Duration of exposure excluding taper off periods** is defined as above but deduct the intervening period without treatment for subjects who taper off and restart after cGvHD recurrence. These periods are captured as dose interruption with reason “dose tapering following response”.

Summary of duration of exposure of investigational treatment in days will include categorical summaries (based on clinically meaningful time intervals) and continuous summaries (i.e. mean, standard deviation etc.) using appropriate units of time.

Duration of exposure to investigational treatment in patient-years

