The total daily dose, actual cumulative dose, DI and RDI up to last date of exposure to study treatment will be summarized.

Dose reductions, interruptions or permanent discontinuations

The number of patients who have dose reduction, or interruptions, and the reasons, will be summarized for ruxolitinib by Age group. Separate summaries will be generated for patients with dose change due to dose tapering (change of dose due to efficacy of treatment) and patients with dose change due to other reasons (potential safety concerns). The number of patients who have dose permanent discontinuations and the reasons will be summarized by Age group.

‘Type of change’ and ‘Dose permanently discontinued’ fields from the Study Treatment CRF pages will be used to determine the dose change, dose interruptions, and permanent discontinuations respectively.

The corresponding fields ‘Reason for Change’ and ‘Reason for Permanent Discontinuation’ will be used to summarize the reasons.

For the purpose of summarizing interruptions and reasons, in case multiple entries for interruption that are entered on consecutive days with different reasons will be counted as separate interruptions. However, if the reason is the same in this mentioned multiple entries on consecutive days, then it will be counted as one interruption.

Dose Reduction: A dose changed when the actual total daily dose is lower than the previous actual total daily dose A dose change due to dose tapering (change of dose due to efficacy of treatment) will not be considered as a dose reduction. Only dose changes that are indicated on the CRF as due to reason other than dose tapering, are taken into consideration. Number of reductions will be derived programmatically based on the change and the direction of the change.

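### SAP 2.13 selects children for the time-to-recurrence analysis by a permanent-discontinuation reason that can miss those who recurred and restarted ruxolitinib

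*SAP*

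**What the plan says.** SAP 2.13 limits the analysis as follows: "This analysis is performed only for patients who taper off ruxolitinib due to achieving a CR or PR". It gives one way to find these children, the reason 'responder' recorded "for ruxolitinib permanent discontinuation on the exposure CRF". The endpoint is worded "Time to recurrence is defined as the time from completion of a taper of systemic therapy until cGvHD recurrence". With fewer than 5 recurrences, "data will be reported in listing only". Table 1-1 in SAP 1.2 describes the endpoint as "Time to recurrence, assessed for patients with completion of a taper of systemic therapy only" and marks it for the final CSR.

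Protocol 6.1.5 lets the investigator restart ruxolitinib after a recurrence. Two other parts of the SAP deal with children who do. SAP 2.1.1 runs their on-treatment period from first to very last dose plus 30 days, "including the period without treatment, which are collected in the database as dose interruption". SAP 2.4.1 subtracts the same gap in one version of exposure duration: "These periods are captured as dose interruption with reason" 'dose tapering following response'. SAP 2.4.1 also names the type-of-change field and the permanent-discontinuation field, which "will be used to determine the dose change, dose interruptions, and permanent discontinuations respectively". Each has its own reason field.

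**The concern.** For a child who tapers off and never restarts, the taper-off is the permanent discontinuation, and 'responder' is the expected reason. For a child who restarts, the first taper-off is stored as an interruption. The permanent discontinuation is then the later, final stop, and its reason may be toxicity, loss of benefit or completion. SAP 2.13 does not refer to the interruption record, so such a child can fall outside the analysis.

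The loss is not random. In SAP 2.1.1 and 2.4.1 the restart follows a recurrence, so the children at risk of being left out all have the event, while event-free children keep the flag. Selection then depends on the outcome, in an analysis meant to show how often and how soon disease returns after ruxolitinib is stopped. Because the population rule applies to the whole analysis, a literal reading would also leave these children out of the fallback listing.

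A smaller point concerns the clock. The heading and selection rule of 2.13 name ruxolitinib, but the endpoint sentence and Table 1-1 name systemic therapy, and no date derivation is given.

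**Working it through.** The plan states no figure for this analysis, so there is none to reproduce. The check applies the 2.13 rule to the records that the SAP describes.

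**Who is selected**

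| Course | How the first taper-off is recorded | Selected under 2.13? |
|---|---|---|
| Tapers off, no recurrence | Permanent discontinuation, 'responder' | Yes |
| Tapers off, recurs, treated with something else | Permanent discontinuation, 'responder' | Yes |
| Tapers off, recurs, restarts, later stops for another reason | Interruption, 'dose tapering following response' | No |
| Tapers off, recurs, restarts, tapers off again for response | Interruption; the final stop is 'responder' | Yes, but 2.13 does not say which taper starts the clock |

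The third row is the defect. The fourth shows why the origin should be stated.

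**Size, by illustration.** The documents do not say how many children tapered off, recurred or restarted. Let n be the number who tapered off, r the number who recurred, and k the number of restarters whom the flag misses. Each missed child leaves both numerator and denominator, so the crude proportion with recurrence is (r − k)/(n − k).

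Assume r = 5, the smallest count at which 2.13 does not fall back to a listing:

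| k missed | n = 10 | n = 20 | Recurrences left |
|---|---|---|---|
| 0 | 5/10 = 50.0% | 5/20 = 25.0% | 5 |
| 1 | 4/9 = 44.4% | 4/19 = 21.1% | 4, listing only |
| 3 | 2/7 = 28.6% | 2/17 = 11.8% | 2, listing only |
| 5 | 0/5 = 0% | 0/15 = 0% | 0, listing only |

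With r = 6 and n = 10, missing one gives 5/9 = 55.6% instead of 60%, and the curve is still drawn. Missing two gives 4/8 = 50.0% and only a listing.

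The k = 5 row is an extreme in which every child with a recurrence restarted and lost the flag. These are crude proportions. The shift in a Kaplan-Meier estimate would also depend on follow-up times.

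**The case against.** The strongest reply is that this is an edge case in a minor analysis. The endpoint is exploratory, was added in the SAP, carries no hypothesis test and is run only if enough children recur. The SAP's exposure rules for restarters are conditional, so there may be none. Whether a restarter's final reason is 'responder' depends on CRF entries that the documents do not show. Protocol 6.1.5 requires recurrences to be reported in the database, and SAP 2.4.1 lists every dose with its change reason, so a missed child remains visible to a careful reader. All of this is fair and limits the reach. It does not make the rule right: a child visible in a dosing listing is still absent from the recurrence estimate. The same SAP also spells out how to handle restarters in 2.1.1 and 2.4.1 but does not do so in 2.13.

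Two stronger readings are tempting, and the documents do not support them. A reader might infer that 2.13 has no workable population at all. It has one for every child who never restarts, including those whose recurrence is treated with another drug. A reader might also infer that restarters would get negative times, because the end of treatment in SAP 2.1.1 is the last nonzero ruxolitinib dose, which for them falls after the recurrence. But 2.13 does not name that date, and SAP 2.5.1 defines recurrence as following the taper-off, so the natural origin is the taper before it. What stands is that the derivation should be written down.

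The wording difference between ruxolitinib and systemic therapy matters less than it seems. Protocol 6.1.5.2 does not allow a ruxolitinib taper before corticosteroids and CNIs are stopped, so ruxolitinib will normally be the last of these to end.

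**Conclusion.** The concern holds in a limited form. The stated selection rule can exclude children because they recurred and restarted. Where it does, recurrence is understated, and a Kaplan-Meier analysis may become a listing. This rests on three things in the documents: restart is allowed, a restarter's first taper-off is stored as an interruption, and 2.13 looks only at permanent discontinuation. It also needs at least one restarter whose final stop was not coded 'responder', which the documents neither confirm nor rule out. The mechanism is certain; the size is unknown, and the percentages above are illustrations only.

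The reach is one exploratory analysis in the final CSR. The primary response rate, the exposure summaries and the on-treatment periods are unaffected. The correction is still worth making, because the error depends on the outcome and costs little to remove.

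**What to change.** In SAP 2.13, with matching wording in Table 1-1:

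- **Population:** subjects with permanent-discontinuation reason 'responder', or with a dose interruption whose reason is 'dose tapering following response'.
- **Origin:** the last nonzero ruxolitinib dose of the first such taper. For a restarter this is the dose before the interruption.
- **Event:** the first recurrence after that date.
- **Wording:** ruxolitinib in place of systemic therapy in both places.

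This takes one or two sentences and no new data, since the reason fields, dosing record and recurrence reports are already collected. The downside is small: a short gap within a taper might carry the same interruption reason. Those few records need a manual check, made without reference to whether the child recurred.
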